#### **5.4.3.4 Abortions**

Any abortion should be classified as a serious adverse event (as the Sponsor considers abortions to be medically significant), recorded on the Adverse Event eCRF, and reported to the Sponsor immediately (i.e., no more than 24 hours after learning of the event; see Section 5.4.2).

#### **5.4.3.5 Congenital Anomalies/Birth Defects**

Any congenital anomaly/birth defect in a child born to a female patient exposed to study treatment or the female partner of a male patient exposed to study treatment should be classified as a serious adverse event, recorded on the Adverse Event eCRF, and reported to the Sponsor immediately (i.e., no more than 24 hours after learning of the event; see Section 5.4.2).

## **5.5 FOLLOW-UP OF PATIENTS AFTER ADVERSE EVENTS**

### **5.5.1 Investigator Follow-Up**

The investigator should follow each adverse event until the event has resolved to baseline grade or better, the event is assessed as stable by the investigator, the patient is lost to follow-up, or the patient withdraws consent. Every effort should be made to follow all serious adverse events considered to be related to study treatment or study-related procedures until a final outcome can be reported.

During the study period, resolution of adverse events (with dates) should be documented on the Adverse Event eCRF and in the patient's medical record to facilitate source data verification.

All pregnancies reported during the study should be followed until pregnancy outcome.

### **5.5.2 Sponsor Follow-Up**

For serious adverse events, non-serious adverse events of special interest, and pregnancies, the Sponsor or a designee may follow up by telephone, fax, electronic mail, and/or a monitoring visit to obtain additional case details and outcome information (e.g., from hospital discharge summaries, consultant reports, autopsy reports) in order to perform an independent medical assessment of the reported case.

## **5.6 ADVERSE EVENTS THAT OCCUR AFTER THE ADVERSE EVENT REPORTING PERIOD**

The Sponsor should be notified if the investigator becomes aware of any serious adverse event that occurs after the end of the adverse event reporting period (defined as 90 days after the last dose of study treatment), if the event is believed to be related to prior study treatment. *The sponsor should also be notified of events of second malignancies after the end of the adverse event reporting period for patients who received obinutuzumab.*

An exception is *for patients receiving obinutuzumab, where Grade 3–4 infections (both related and unrelated) should be reported until up to 2 years after the last dose of study treatment.*

The investigator should report these events directly to the Sponsor or its designee, either by faxing or by scanning and emailing the Serious Adverse Event/Adverse Event of Special Interest Reporting *Form* using the fax number or email address provided to investigators.

During survival follow-up, deaths attributed to progression of lymphoma should be recorded only on the Study Completion/Early Discontinuation eCRF.

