### **1.2.2.2 Clinical Safety of Obinutuzumab**

As of 4 July 2016, an estimated 3636 patients with B-cell lymphoma (including DLBCL, indolent B-cell lymphoma, and CLL) had been treated with obinutuzumab given as monotherapy or in combination with CHOP, bendamustine, fludarabine plus cyclophosphamide, or chlorambucil, at doses ranging from 50 to 2000 mg. Overall, the safety of obinutuzumab monotherapy and obinutuzumab combination therapy was manageable.

The most frequent causes of death were disease progression and adverse events associated with infectious diseases. This is consistent with the study population and the disease under treatment. In Study GAO4768g (obinutuzumab 1000 mg vs. 2000 mg), the incidence of deaths did not increase with increased obinutuzumab dose (7.5% and 2.6%, respectively).

Of particular interest, a high incidence of infusion-related reactions (IRRs) was observed consistently in all obinutuzumab trials. The reported incidence of IRRs varied across studies. In the CLL population, the incidence ranged from 66% in previously untreated

patients receiving obinutuzumab plus chlorambucil (Study BO21004) to 100% in patients with R/R disease who received obinutuzumab monotherapy (pooled data from Studies BO21003 and BO20999, CLL cohorts).

In the B-cell lymphoma population, the incidence of IRRs in studies of obinutuzumab monotherapy was 75.1% (pooled data from Study BO21003 and from high-dose B-cell lymphoma cohorts from Study BO20999). In studies of obinutuzumab in combination with either CHOP (Study GAO4915g) or bendamustine (Study BO21000), the incidence of IRRs, regardless the relationship with obinutuzumab, was 70%–78%.

Other important risks associated or potentially associated with obinutuzumab are tumor lysis syndrome (TLS), thrombocytopenia (including acute thrombocytopenia), neutropenia, prolonged B-cell depletion, infections (including progressive multifocal leukoencephalopathy [PML] and hepatitis B virus [HBV] reactivation), worsening of preexisting cardiac conditions, gastrointestinal (GI) perforation, impaired immunization response, immunogenicity, and second malignancies. The important identified risks associated with obinutuzumab are presented in detail in Section 5.1.1 of this protocol and in the Obinutuzumab Investigator's Brochure.

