## **3.2 END OF STUDY AND LENGTH OF STUDY**

The end of this study is defined as the time when both of the following criteria are met:

- All enrolled patients with FL have *been followed for at least 90 days after they have completed or discontinued study treatment (including induction treatment and maintenance treatment as applicable)*.
- All enrolled patients with DLBCL have been followed for at least 1 year after they have completed or discontinued study treatment (including induction treatment and consolidation treatment as applicable).

The total length of the study, from screening of the first patient to the end of the study, is expected to be approximately 5 years.

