#### **5.1.4.11 Second Primary Malignancies**

Patients with multiple myeloma treated with lenalidomide in studies that included melphalan and SCT had a higher incidence of second primary malignancies, particularly acute myelogenous leukemia and Hodgkin's lymphoma. Patients are to be monitored for the development of second malignancies.

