### **5.4.2.2 Events that Occur after Study Treatment Initiation**

After initiation of study treatment, serious adverse events and adverse events of special interest will be reported until 90 days after the last dose of study treatment. *After this period, the investigator should report any serious adverse events that are believed to be related to prior study treatment (see Section 5.6).* DLTs will be reported during the DLT assessment window. Investigators should record all case details that can be gathered immediately (i.e., within 24 hours after learning of the event) on the Adverse Event eCRF and submit the report via the electronic data capture (EDC) system. A report will be generated and sent to Roche Safety Risk Management by the EDC system.

In the event that the EDC system is unavailable, the Serious Adverse Event/Adverse Event of Special Interest Reporting Form provided to investigators should be completed and submitted to the Sponsor or its designee immediately (i.e., no more than 24 hours after learning of the event), either by faxing or by scanning and emailing the form using the fax number or email address provided to investigators. Once the EDC system is available, all information will need to be entered and submitted via the EDC system.

Instructions for reporting *events after the adverse events reporting period* are provided in Section 5.6.

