### Schedule of Assessments for Patients with Diffuse Large B-Cell Lymphoma (cont.)

---

- z After informed consent has been obtained but prior to initiation of study treatment, only serious adverse events caused by a protocol-mandated intervention should be reported. After initiation of study treatment, all adverse events will be reported until 90 days after the last dose of study treatment. After this period, the Sponsor should be notified if the investigator becomes aware of any serious adverse event that is believed to be related to prior study treatment (see Section 5.6). The investigator should follow each adverse event until the event has resolved to baseline grade or better, the event is assessed as stable by the investigator, the patient is lost to follow-up, or the patient withdraws consent. Every effort should be made to follow all serious adverse events considered to be related to any of the study treatment components or trial-related procedures until a final outcome can be reported.
- aa The screening PET-CT scan must be performed within 35 days prior to Day 1 of Cycle 1.
- bb Perform only for patients who have received at least two cycles of induction treatment.
- cc Includes CT scan of the neck (if clinically indicated), chest, abdomen, and pelvis. If contrast is medically contraindicated (e.g., patients with contrast allergy or impaired renal clearance), MRI scans of the chest, abdomen, and pelvis (and neck, if clinically indicated) and a non-contrast CT scan of the chest may be performed. Combined PET/CT scanners may be used to collect diagnostic CT scans, but only according to the technical guidelines in the imaging manual. The screening CT scan must be performed within 35 days prior to Day 1 of Cycle 1.
- dd Perform within 7 days prior to Day 1 of Cycle 3.
- ee Perform only if not done within the previous 3 months.
- ff Perform every 6 months.
- gg Bone marrow biopsy and aspirate must be performed within approximately 3 months prior to Day 1 of Cycle 1.

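### Second malignancies after 90 days must be reported only for obinutuzumab-treated (FL) patients, although the lenalidomide risk and the AESI status also cover the DLBCL group

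*Combined protocol and SAP*

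**What the plan says.** - **The late rule.** Section 5.6 says: "The sponsor should also be notified of events of second malignancies after the end of the adverse event reporting period for patients who received obinutuzumab". Section 5.3.1 has the same rule with the same limit.
- **The general rule after 90 days.** Section 5.6 asks for serious adverse events only. It describes the period and the condition as "defined as 90 days after the last dose of study treatment), if the event is believed to be related to prior study treatment".
- **The lenalidomide risk.** Section 5.1.4.11 reports that myeloma patients given lenalidomide in studies that included melphalan and stem-cell transplantation "had a higher incidence of second primary malignancies". It then instructs: "Patients are to be monitored for the development of second malignancies". Neither antibody nor histology limits that instruction.
- **The obinutuzumab risk.** Section 1.2.2.2 ends its list of risks associated or potentially associated with obinutuzumab with "impaired immunization response, immunogenicity, and second malignancies".
- **Status of the event.** Section 5.2.3 lists second malignancies as an adverse event of special interest (AESI) for the study as a whole.
- **Reporting mechanics.** Section 5.4.2.2 says "serious adverse events and adverse events of special interest will be reported until 90 days after the last dose of study treatment". After that it asks for related serious events and refers to Section 5.6. Appendix 2 footnote z (DLBCL) says "After this period, the Sponsor should be notified if the investigator becomes aware of any serious adverse event that is believed to be related". The footnote also cites Section 5.6.
- **Follow-up.** Section 3.2 requires that "All enrolled patients with DLBCL have been followed for at least 1 year after they have completed or discontinued study treatment".

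**The concern.** The extension follows obinutuzumab, but the only subsection of the safety plan (Section 5.1) devoted to second malignancies is the lenalidomide one, and both groups take lenalidomide. A DLBCL patient therefore carries the named risk, falls under the monitoring instruction and the AESI listing, and loses unconditional reporting at day 90.

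Two things are at stake. First, late DLBCL cases reach the Sponsor only through the investigator's judgment of relatedness, which can only lower the count. Second, Section 6.5 summarizes AESIs by histology in the expansion phase. The FL figure would include late cases whatever their attribution, and the DLBCL figure would not. A reader setting the two side by side could not separate a difference between regimens from a difference in collection.

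**Working it through.** The plan states no figure to reproduce. The check is a comparison of provisions, followed by simple arithmetic for the size of the gap.

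**Who is covered after day 90**

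| Provision | FL (G+Pola+Len, then G+Len) | DLBCL (R+Pola+Len, then R+Len) |
|---|---|---|
| Receives lenalidomide (Tables 4, 5, 9, 10) | Yes | Yes |
| Monitoring instruction, 5.1.4.11 | Applies | Applies |
| AESI, 5.2.3 | Applies | Applies |
| Reportable regardless of relatedness up to 90 days, 5.4 and 5.4.2.2 | Yes | Yes |
| Reportable after 90 days regardless of relatedness, 5.3.1 and 5.6 | Yes | No |
| Reportable after 90 days if serious and believed related, 5.6 | Yes | Yes |
| Minimum post-treatment follow-up, 3.2 | 90 days | 1 year |

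The groups differ only in the late-reporting row and the follow-up row, and these run in opposite directions. The group with the late rule has the shorter required follow-up. The group without it has the longer.

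**Where the gap comes from**

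The limiting words are in Sections 5.3.1 and 5.6. Appendix 2 footnote z agrees with Section 5.6 as written, because DLBCL patients receive no obinutuzumab. The footnote reflects the gap and does not create it. For FL, Section 5.4.2.2 and Appendix 1 footnote aa do not name late second malignancies; footnote aa names only Grade 3 and 4 infections as a late exception. Both refer to Section 5.6, where the FL rule stands. That is incomplete repetition, not loss of the rule.

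**Size**

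- Planned DLBCL patients (Section 6.1): 40 + 12 = 52 to 40 + 18 = 58.
- Share of planned enrollment of 110–128, at matching ends of the ranges: 52/110 = 47% and 58/128 = 45%.
- Minimum post-treatment follow-up without unconditional reporting, for a DLBCL patient followed the full year: 365 − 90 = 275 days.

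**The same gap over the whole observation period**

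For a DLBCL patient who completes treatment on schedule:

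- Cycle 6 Day 1 is day 1 + 5 × 28 = 141.
- Consolidation starts 8 weeks later, on day 141 + 56 = 197.
- Month 6 Day 1 is day 197 + 5 × 28 = 337, so the last lenalidomide dose (Day 21) falls on day 357.
- Unconditional reporting ends on day 357 + 90 = 447.
- One year of follow-up ends on day 357 + 365 = 722.
- Covered: 447/722 = 62% of observed days. Not covered: 275/722 = 38%.

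**The case against.** The strongest reply is that the limit is deliberate. It is worded consistently in Sections 5.3.1 and 5.6. Second malignancies appear among the obinutuzumab risks in Section 1.2.2.2 and are absent from the rituximab risks in Section 5.1.2. The lenalidomide evidence is from myeloma with melphalan and transplantation, a different setting. Serious related cases remain reportable without time limit, and Section 5.3.4 tells investigators to weigh known associations when they judge causality. No FL-versus-DLBCL safety comparison is planned, and no primary endpoint or dose decision is touched.

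Much of this stands. The limit may well track the obinutuzumab profile, and the lenalidomide evidence is indirect. But a reason to include FL is not a reason to exclude DLBCL. The protocol applies its own monitoring instruction and AESI listing to everyone who takes lenalidomide, and it gives no rationale for stopping earlier in one group. The relatedness route is the filter at issue, so it does not answer the point. Sponsor upgrading of causality under Section 5.7 can act only on cases that have been received.

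Three stronger readings are tempting, and the documents do not support them:

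- **That a 90-day window misses most second malignancies.** The documents give no latency or incidence.
- **That three-quarters of late cases are lost, since 275/365 = 75%.** That is a share of post-treatment days, not of events.
- **That the reporting text and schedules drop the rule and so cause the DLBCL gap.** Section 5.3.1 carries the rule, and Section 5.4.2.2 and both footnotes point to Section 5.6.

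**Conclusion.** The point holds as a mismatch of scope. After day 90, second malignancies in the 52–58 planned DLBCL patients are reportable only if serious and believed related. The risk statement, monitoring instruction and AESI listing all cover these patients, and their follow-up continues for at least 275 further days. The consequence is attribution-filtered capture in DLBCL and by-histology summaries collected under unequal rules. How many cases this would affect cannot be estimated from the documents.

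The conclusion rests on these assumptions:

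- Only FL patients receive obinutuzumab, as in the current design.
- The year of follow-up in Section 3.2 applies and is counted from about the last dose. Appendix 2 footnote d defines the end of study without that year, so the 275 days depend on Section 3.2 governing.
- The patient is followed for the full year. After progression, follow-up covers only survival and new anti-lymphoma treatment, every 3 months.

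This is an inexpensive improvement to safety capture. It does not threaten the efficacy conclusions.

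**What to change.** In Sections 5.3.1 and 5.6, require notification of second malignancies after the 90-day period, regardless of attribution, for all patients who received lenalidomide. That covers both groups. Put the same sentence into Section 5.4.2.2, Appendix 1 footnote aa and Appendix 2 footnote z, so that a site working from the schedule sees it without following a cross-reference. If the Sponsor prefers to keep the present limit, state the reason for leaving DLBCL out, and note in the AESI tables that late cases were collected under different rules in the two groups.

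The cost is an amendment of a few sentences plus a report form for each case a site learns of, which I assume will be few. No visit is added, because DLBCL patients already have contact every 3 months. The change does not add an active search for cases: after progression it still depends on the site becoming aware of one.

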## 5.7 EXPEDITED REPORTING TO HEALTH AUTHORITIES, INVESTIGATORS, INSTITUTIONAL REVIEW BOARDS, AND ETHICS COMMITTEES

The Sponsor will promptly evaluate all serious adverse events and non-serious adverse events of special interest against cumulative product experience to identify and expeditiously communicate possible new safety findings to investigators, IRBs, ECs, and applicable health authorities based on applicable legislation.

To determine reporting requirements for single adverse event cases, the Sponsor will assess the expectedness of these events using the following reference document:

- Obinutuzumab Investigator's Brochure (Oncology)
- *Rituximab Investigator's Brochure (Oncology)*
- Polatuzumab Vedotin Investigator's Brochure
- Lenalidomide SmPC

The Sponsor will compare the severity of each event and the cumulative event frequency reported for the study with the severity and frequency reported in the applicable reference document.

Reporting requirements will also be based on the investigator's assessment of causality and seriousness, with allowance for upgrading by the Sponsor as needed.

## 6. STATISTICAL CONSIDERATIONS AND ANALYSIS PLAN

This Phase Ib/II, open-label, multicenter, non-randomized study will evaluate the safety, efficacy, and pharmacokinetics of G+Pola+Len in patients with R/R FL *and R+Pola+Len in patients with R/R DLBCL*.

The study will include an initial dose-escalation phase followed by an expansion phase. The dose-escalation phase *in* FL patients is designed to determine the RP2Ds for both polatuzumab vedotin and lenalidomide when combined with fixed doses of obinutuzumab. *The dose-escalation phase in DLBCL patients is designed to determine the RP2D of lenalidomide when combined with fixed doses of polatuzumab vedotin (1.8 mg/kg) and rituximab (375 mg/m^2).* During the expansion phase, additional patients with R/R FL or DLBCL will undergo treatment with polatuzumab vedotin and lenalidomide at their respective RP2Ds in combination with obinutuzumab *or rituximab*.

Study data will be summarized separately for each phase. Data from the dose-escalation phase will be summarized by cohort (assigned dose level). Data from the expansion phase will be summarized by histologic subtype (i.e., FL or DLBCL). Data will be summarized as warranted, and listings will be used in place of tables when the sample sizes are small.

## 6.1 DETERMINATION OF SAMPLE SIZE

Limited dose finding will be conducted during the dose-escalation phase of this study. The estimated sample size follows from the dose-escalation rules for a standard 3+3 algorithm, as outlined in Section 3.1. It is anticipated that enrollment of 5 cohorts of 3–6 patients each, for a total of 18–30 patients, will be required to establish the RP2D during the dose-escalation phase *for patients with R/R FL. An additional 3 possible cohorts of 3–6 patients each, for a total of 12–18 patients will be required to establish the RP2D during the dose-escalation phase for patients with R/R DLBCL.*

Approximately 80 patients (40 patients with FL and 40 patients with DLBCL) will be enrolled during the expansion phase. Overall, approximately 110–128 patients will be enrolled in the study.

The primary efficacy analysis will be the estimation of the true proportion of patients expected to obtain a PET-CT–defined CR at EOI.

Data from completed and ongoing studies in similar disease settings will be used as historical controls for comparison. Currently available data indicate that the historical CR rate based on PET-CT scans is 40% for R/R FL and DLBCL.

A sample size of 40 patients is deemed sufficient to provide adequate precision for the point estimate and for the lower bound of the two-sided 90% CI to rule out a clinically uninteresting probability of response of <55%, assuming an observed PET-CT–defined CR rate of 70%.

Table 22 lists the two-sided 90% Clopper-Pearson exact CIs for the true probability of achieving a PET-CT–defined CR at EOI for a range of observed proportions based on a sample of 40 patients.

**Table 22 Potential 90% CI for the True Probability of Achieving a PET-CT–Defined Complete Response at End of Induction**

Observed Proportion of Patients Who Achieve a PET-CT–Defined CR at EOI	Two-Sided 90% Clopper-Pearson CI a for True Population PET-CT–Defined CR
0.50	(0.36, 0.64)
0.55	(0.40, 0.68)
0.60	(0.46, 0.73)
0.65	(0.51, 0.77)
0.70	(0.56, 0.82)
0.72	(0.58, 0.83)
0.75	(0.61, 0.86)
0.80	(0.66, 0.89)
0.85	(0.72, 0.93)

CI = confidence interval; CR = complete response; CT = computed tomography; EOI = end of induction; PET = positron emission tomography.

a Note that the lower limit of a two-sided 90% CI is equivalent to a one-sided 95% CI.

## 6.2 DEFINITION OF ANALYSIS POPULATIONS

The following populations are defined:

- The primary safety and efficacy populations will include patients who received at least one dose of any component of the combination.
- The intent-to-treat population will include all patients enrolled in the study.

